11.1 ADVERSE EVENTS

Adverse events will be coded by SOC and preferred term using the Medical Dictionary for Regulatory Activities.

For a given AE and patient, if more than 1 severity grade is reported, the worst severity grade (the greater of the onset and maximum severity recorded on the electronic case report from [eCRF]), will be used for analysis.

Adverse events will be classified into ocular AEs and nonocular AEs. An ocular AE will be determined as indicated on the AE form of eCRF, and thus are not limited to AEs with primary SOCs of eyes. The treatment-related ocular AEs will be further broken down by either related to injection procedure or related to study drug as indicated on eCRF. Ocular AEs will be tabulated by treatment group for the study eye and pooled for the fellow eye, and nonocular AEs will be summarized by treatment group for patient. Analysis by cycle of treatment will also be performed.

Treatment-Emergent Adverse Events

An AE will be considered a treatment-emergent adverse event (TEAE) for the study treatment period if the AE meets 1 of the following criteria:

- The onset date is on or after the first study treatment date.
- The onset date is before the first study treatment date and either:
 - The severity of the event worsened on or after the first treatment date.
 - The event became serious on or after the first study treatment date.

An AE will be considered as a TEAE for a treatment cycle if the AE meets 1 of the following criteria:

- The onset date is on or after the treatment administration of the cycle but prior to the next cycle administration.
- The onset date is before the treatment administration of the cycle and either:
 - The severity of the event worsened on or after the treatment administration of the cycle.
 - The event became serious on or after the treatment administration of the cycle.

Overall summary of TEAEs will be provided on a per-patient basis for categories of all TEAEs, treatment-related TEAEs, injection procedure-related TEAEs, study drug-related TEAEs, serious TEAEs (STEAEs), deaths, and TEAEs leading to study discontinuation. Each category (except deaths) will be further classified into ocular and nonocular subcategories.

The number and percentage of patients reporting TEAEs will be provided on a per-patient basis by 1) SOC and preferred term; 2) SOC, preferred term and severity in descending order of frequency for each treatment group.

The number and percentage of patients reporting nonocular TEAEs in each treatment group will be tabulated by SOC and preferred term. Also the number and percentage of patients reporting treatment-related (including study drug related or injection procedure related) nonocular TEAEs in each treatment group will be tabulated by SOC and preferred term.

Similar analyses will be done for ocular TEAEs including 1) by PT and severity; 2) treatment-related TEAEs by PT for each treatment group by study eye and fellow eye. In addition, similar analyses will be performed for ocular TEAEs by treatment cycle.

Within each treatment cycle, ocular TEAEs identified (onset or worsened) within 2 days of administration and identified more than 2 days of administration of each cycle will be summarized by each treatment group for study eye and pooled for fellow eye.

Serious TEAEs

Nonocular and ocular STEAEs will be summarized by preferred term and treatment group, respectively.

TEAEs Leading to Study Discontinuation

Nonocular TEAEs and ocular TEAEs leading to premature discontinuation of the study will be summarized by preferred term and treatment, respectively.

Similarly, ocular TEAEs leading to premature discontinuation will also be tabulated by treatment group by treatment cycle.

Ocular TEAEs Leading to Study Drug Discontinuation or Regimen Change

Ocular TEAEs leading to study drug discontinuation will be summarized by preferred term and treatment for the entire study period and also for each cycle. Ocular TEAEs leading to study drug discontinuation or regimen change are defined as the ocular TEAEs with action regarding study drug reported as “Discontinued” or “Regimen Changed” on the eCRF AE form.

Ocular TEAEs Leading to Implant Removal

Ocular TEAEs leading to implant removal will be summarized by preferred term and treatment for the entire study period and also for each cycle.

TEAEs of Special Interest

Corneal TEAEs and Anterior chamber inflammation TEAEs of interest will be summarized by preferred term and treatment group, respectively. Similar analyses will be done by treatment cycle. The full list of corneal AEs and Anterior chamber inflammation AEs of interest will be provided prior to each database lock.

Additional subcategory of TEAEs may be analyzed separately, such as for ocular TEAE associated with use of a prostaglandin analog (PGA), etc.

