4.4 Exclusion Criteria

[figure not shown]

The following are criteria for exclusion from participating in the study:

Non-ocular Criteria for Exclusion

- 1. Uncontrolled systemic disease
- 2. Female patients who are pregnant, nursing, or planning a pregnancy, or who are of childbearing potential and not using a reliable means of contraception during the study (see Section 4.5.3)
- 3. Known allergy or sensitivity to any study medication or its components, any component of the delivery vehicle, procedure-related materials, or diagnostic agents used during the study (eg, topical anesthetic, dilating drops, fluorescein)
- 4. Contraindications to beta-blocker therapy 

[figure not shown]
Approval Date: 05-Jun-2018

[figure not shown]
- 
5. Any condition which would preclude the patient's ability to comply with study requirements, including completion of the study
 6. Patients who have a condition or are in a situation which, in the investigator's opinion, may put the patient at significant risk, may confound the study results, or may interfere significantly with the patient's participation in the study
 7. Anticipated use of oral, intramuscular, or intravenous corticosteroids from 2 months prior to the Baseline visit through Week 52
 8. Concurrent or anticipated enrollment in an investigational drug or device study or participation in such a study within 2 months prior to the Baseline visit through the final study visit
 9. Previous enrollment in another Allergan Bimatoprost SR study
- 

Ocular Criteria for Exclusion

[figure not shown]
11. In the investigator's opinion, patient is nonresponsive to topical ophthalmic beta-blockers and/or topical prostamides, prostaglandins, or prostaglandin analogs (eg, LUMIGAN, Xalatan, Travatan)
12. History or evidence of clinically relevant, substantial ocular trauma (eg, a traumatic cataract, traumatic angle recession, etc) in the study eye
13. The following surgical history:
 - a. History or evidence of complicated cataract surgery in the study eye: eg, surgery resulting in complicated lens placement (such as anterior chamber intraocular lens implant [IOL], sulcus IOL, aphakia, etc) or intraoperative complications (such as a posterior capsular tear [with or without vitreous loss], substantial iris trauma, etc). Note: history of uncomplicated cataract surgery is not an exclusion.

- b. History of phakic IOL insertion for refractive error correction in the study eye

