6.2 Safety Measures

The following will be collected and recorded on the appropriate eCRF page(s):

Adverse Events: All adverse events, from the moment the patient signs the informed consent form, will be monitored and recorded in the patient's source documents. All events will be reported to Allergan on an adverse event eCRF, including seriousness, severity, action taken and relationship to study drug. If adverse events occur, the first concern will be the safety of the study patient.

Weight and Height: Weight will be measured in pounds (lb) or kilograms (kg) using a scale. Height will be measured in inches (in) or centimeters (cm). Height and weight will be measured at screening as part of the demographic data; historical patient information and/or patient reports should not be used for either measurement.

Vital signs: Systolic and diastolic blood pressure and pulse rate will be measured after patients have been at rest (seated) for at least 5 minutes. Body temperature will be measured orally (or with an infrared forehead thermometer) and recorded as $^{\circ}\text{F}$ or $^{\circ}\text{C}$.

Hematology, blood chemistry, and urinalysis: Blood and urine samples will be collected for blood chemistry and hematology panels and urinalysis.

Pregnancy: Females of childbearing potential will have pregnancy tests performed. Pregnancy test kits will be provided by Covance Central Laboratory Services or a designated regional laboratory and will be administered according to the instructions provided with the tests.

Measures of ocular safety include:

Visual Acuity: Visual acuity tests will be performed at all scheduled visits except on any of the 3 administration days. Manifest refraction using Snellen equivalent with a logMar chart (see Protocol Procedure Manual) will be performed at Screening, Baseline, Weeks 12 and 52, and Month 20/Exit. At all other visits, the visual acuity technician will use the last manifest refraction performed and determine the Snellen equivalent visual acuity using the logMar chart. If there is a 2-line or more reduction in visual acuity from the last BCVA performed, a repeat manifest refraction in both eyes and BCVA will be performed.

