8.9 Withdrawal Criteria

After the first administration (or Sham), failure to undergo an Administration Day visit does not indicate total withdrawal from the study. Patients who have received nonstudy IOP-lowering medication in only one eye will continue through the duration of the study. Patients who have received nonstudy IOP-lowering medication in both eyes, or patients who do not undergo Cycle 2 or 3 (or both) Administration Visits, will still be followed for 12 months after the last Bimatoprost SR or Sham administration for safety reasons. These patients are eligible for Early Discontinuation (Early Exit) as described in Section 8.8, above.

The investigator should consider withdrawing a patient from the study early if any of the following criteria are met:

- Patient develops (or has an exacerbation of) a medical condition that, in the opinion of the investigator, compromises the patient's ability to participate in the study
- Patient develops (or has an exacerbation of) a medical condition that, in the opinion of the investigator, compromises the patient's ability to participate in the study
- Patient is unwilling or unable to continue to comply with study procedures
- Patient is unwilling or unable to continue in the study

If a patient develops (or has an exacerbation of) a medical condition that, in the opinion of the investigator, would put the patient at an unacceptable medical risk by continuing study participation, the patient will be withdrawn from the study.

Whenever possible, the decision to withdraw a patient from the study or study treatment should be discussed with Allergan.

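### Adverse events that stop or change study drug are summarised only when ocular, so a nonocular event that does this without study exit is identified in no planned action-taken summary

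*SAP*

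**What the plan says.** SAP 11.1 has two relevant summaries of events by the action they led to.

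- **Leaving the study.** "Nonocular TEAEs and ocular TEAEs leading to premature discontinuation of the study will be summarized by preferred term and treatment, respectively". The overall summary carries the same category, in a list that ends with "serious TEAEs (STEAEs), deaths, and TEAEs leading to study discontinuation". Every category in that list except deaths is split into ocular and nonocular.
- **Stopping or changing study drug.** "Ocular TEAEs leading to study drug discontinuation will be summarized by preferred term and treatment for the entire study period", and for each cycle. The category is "defined as the ocular TEAEs with action regarding study drug reported as" discontinued or regimen changed on the eCRF. The subheading, the planning sentence and the definition are all confined to ocular events. The overall summary has no row for this action. The subheading and definition include regimen change, but the planning sentence names discontinuation only.

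Protocol 6.2 has every adverse event reported on the eCRF, "including seriousness, severity, action taken and relationship to study drug", with no distinction between ocular and nonocular. Protocol 8.9 states that, after the first administration, "failure to undergo an Administration Day visit does not indicate total withdrawal from the study". Protocol 5.10 allows readministration to be withheld because of earlier adverse events or safety concerns and does not limit these to the eye.

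**The concern.** A summary of events that end study participation is enough only if stopping treatment and leaving the study are the same thing. Here they are not, because a patient can stop treatment and stay for follow-up. The SAP allows for this by planning a separate study-drug summary, but for one class of event only.

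The omitted class is relevant. The comparator is a beta-blocker, and the protocol lists "Contraindications to beta-blocker therapy" among its nonocular exclusions, so it recognises systemic risk. Control patients use timolol in both eyes and Bimatoprost SR patients use it in the fellow eye. Whether an event was troublesome enough to stop treatment is a standard measure of tolerability and bears on the trial's own safety objective. For nonocular events the SAP text shows it only when the patient also left the study.

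**Working it through.** No arithmetic applies, because the point rests on no sample size, power, error rate or event count. The check is to take one case, a nonocular TEAE that stops or changes study drug in a patient who remains in the study, and ask which planned outputs would show it.

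**Step 1. Can the case arise?** Yes. Protocol 8.9 keeps patients who miss an administration in follow-up, and Protocol 5.10 allows an adverse event of any type to be the reason. Protocol 8.9 also refers to withdrawal from the study and from study treatment as separate decisions.

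**Step 2. Which outputs capture it?**

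| Planned output | Ocular | Nonocular | Shows the case? |
|---|---|---|---|
| TEAEs ending study participation (SAP 11.1) | yes | yes | No, the patient stays |
| TEAEs stopping or changing study drug (SAP 11.1) | yes | no | No, ocular only |
| TEAEs leading to implant removal (SAP 11.1) | yes | no | No, ocular by nature |
| Overall TEAE summary (SAP 11.1) | yes | yes | Event counted; no study-drug action row |
| Nonocular TEAEs, all and treatment-related (SAP 11.1) | – | yes | Event counted; action not shown |
| Serious TEAEs (SAP 11.1) | yes | yes | Only if serious; action not shown |
| Disposition (SAP 7.0) | yes | yes | No, adverse-event reasons are split only for premature discontinuation |
| Exposure (SAP 9.1) | – | – | Number of administrations only, without reasons |
| Vital signs (SAP 11.2) | – | – | No link to stopping treatment |

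**Step 3. Does disposition close the gap by another route?** No. Under SAP 7.0 a patient who received the injection of a cycle, missed the next one and completed extended follow-up counts as a completer of that cycle. In the text available, SAP 9 has no analysis of stopping the drops.

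**Step 4. Is the information collected?** Yes. Protocol 6.2 records action taken for every event, and the SAP already uses that field for ocular events.

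**Result.** The event is counted as a nonocular TEAE, but no action-taken summary in the SAP text identifies it as having stopped or changed treatment. This is the same in all three arms.

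**The case against.** The strongest reply is that systemic events are well covered. By treatment group the SAP plans nonocular TEAEs, treatment-related nonocular TEAEs, nonocular serious TEAEs and nonocular TEAEs ending study participation, and it summarises pulse and blood pressure by visit. Only one attribute of the event is missing. The ocular table is labelled as ocular, is descriptive, and carries no test or claim. Protocol 7.3.4 asks for tables of all and of treatment-related events and requires none by action taken, so the SAP contradicts nothing.

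All of that stands, and it limits the point. A reader might infer that the tolerability comparison with timolol is one-sided, or that systemic reasons for stopping timolol go uncounted. The documents do not support either reading. The events are tabulated by arm, and those that lead to study exit are tabulated with that action. Every arm receives timolol, so the missing contrast is bilateral against unilateral timolol exposure, not timolol against none. The documents give no rate of nonocular treatment stopping, so neither a size nor a direction of distortion can be claimed.

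Further limits also stand:

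- The sentence quoted from Protocol 8.9 concerns missed administrations, not stopping drops. The same section withdraws from the study any patient for whom continuing carries unacceptable medical risk, and such events would enter the study-discontinuation table.
- Excluding patients with beta-blocker contraindications should make these events less frequent.
- Table specifications are in a separate document (SAP 4.0), and SAP 11.1 allows further TEAE subcategories. The finding is that the SAP text does not plan this summary, not that none will be produced.

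None of this supplies the missing summary. The restriction to ocular events is written explicitly, and the general nonocular tables cannot show which events stopped treatment.

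**Conclusion.** The point holds as an omission in the planned safety summaries. SAP 11.1 reports study-drug discontinuation or regimen change for ocular events only, so a nonocular event with that consequence and no study exit is not identified as such in any planned action-taken summary, in any arm. The overall safety comparison is incomplete on this attribute.

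The number of patients affected is unknown. It could be small, since only nonocular events that affect treatment without ending participation are concerned. The primary inference, type I error, power and safety data capture are untouched. The conclusion assumes that the unseen table specifications follow the SAP text and that the action field is completed for nonocular events as Protocol 6.2 describes. It is a cheap improvement that serves the trial's safety objective.

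**What to change.** In SAP 11.1:

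1. Drop the word *Ocular* from the subheading and the definition of the study-drug category, so that it covers all TEAEs whose recorded action is *Discontinued* or *Regimen Changed*.
2. Tabulate nonocular as well as ocular events by preferred term and treatment group, for the whole study and by cycle, from the same eCRF field.
3. Name regimen change in the planning sentence, to match the subheading and definition.
4. Add the category, with ocular and nonocular rows, to the overall TEAE summary.

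The cost is SAP wording and slight extra programming: one more table and one more summary category, with no new data collection. One limitation should be stated with the table. The SAP describes a single action field for study drug, and the documents do not show whether it separates implant from eye drops or one eye from the other. The table may therefore not isolate stopping of timolol.

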11.2 VITAL SIGNS

Descriptive statistics for vital signs (systolic and diastolic blood pressures [mm Hg], pulse rate [bpm], and temperature [Celsius]) at baseline and changes from baseline values at each scheduled follow-up visit will be presented by treatment group.

11.3 OTHER SAFETY PARAMETERS

11.3.1 Implant/Sham Assessment (Postadministration Evaluation)

Implant/sham assessment after the administration of study treatment on each administration day will be summarized by treatment cycle. Number and percent of patient eyes (study eye) will be tabulated by treatment group (Bimatoprost 10 µg and Bimatoprost 15 µg) by the following categories:

- Implant visible in the anterior chamber after the injection
- Implant immediately release from the applicator needle
- Implant release from the applicator needle before the applicator was withdrawn from the eye
- Implant track back and remained attached to the corneal injection site (further classified the maneuvers performed to release the implant into 3 categories: tap on surface of cornea, use of Wilson Anterior Chamber Probe, and other)
- Wound leak with excessive loss in the anterior chamber volume
- Eye patched after injection procedure
- Anterior chamber formed before the patient was released

11.3.2 Best Corrected Visual Acuity

Best corrected visual acuity (BCVA) will be measured for both eyes using the logMar chart at all scheduled visits except on the 3 administration days. BCVA will be recorded in Snellen equivalent units. The line change from baseline at each follow-up evaluation will be calculated using the following formula:

$$\text{Line change} = 10 \times [\log_{10} (20/d_{\text{follow-up}}) - \log_{10} (20/d_{\text{baseline}})]$$

where d_{baseline} = denominator of the Snellen equivalent unit at baseline,
 $d_{\text{follow-up}}$ = denominator of the Snellen equivalent unit at follow-up

The logarithmic values are to be rounded to the nearest tenth before calculation of the line change. A positive value indicates an improvement and a negative value indicates a worsening. For example, the line change for a Snellen equivalent unit at baseline of 20/25 followed by a Snellen equivalent unit of 20/80 at follow-up would be the following:

$$\text{Line change} = 10 \times [\log_{10}(20/80) - \log_{10} (20/25)] = 10 \times (0.1 - 0.6) = -5$$

which represents a worsening of 5 lines in visual acuity.

The data for the worst line change from baseline across follow-up will be summarized by treatment group for study eye and pooled for fellow eye. The worst line change is defined as the greatest decrease from baseline in the number of lines read. Summary statistics of the worst line change will be presented in each of the following categories: worsening (< -2), no changes (≥ -2 and ≤ 2), and improving (> 2). The number and percentage of patient eyes in each category will be presented. Similar analyses will be conducted by treatment cycle.

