1.3.3 Clinical Study with Bimatoprost SR

Study 192024-041D was a Phase 1/2, paired-eye comparison evaluating the safety and efficacy of 4 dose strengths of Bimatoprost SR (6 µg, 10 µg, 15 µg, or 20 µg [2 × 10 µg implants]), as single or repeat administration in one eye (study eye), versus the use of topical LUMIGAN[®] 0.03% in the fellow eye (nonstudy eye). The objective of this study was to evaluate the safety and IOP-lowering efficacy of Bimatoprost SR in patients with OAG.

A total of 109 patients received a single administration and 24 patients received a repeat administration of Bimatoprost SR. A trend in dose-response was observed across the 4 dose strengths that were tested. Data suggest that the implant may provide topical prostaglandin analog-like efficacy up to 3 to 4 months post-implantation in the majority of patients. Data following the second administration in the redosed patients showed similar IOP lowering to that observed following the first administration of Bimatoprost SR.

Bimatoprost SR showed an acceptable safety profile with single and repeat administrations in Study 192024-041D. Most adverse events were ocular, mild or moderate in severity, occurred within the first 2 days after Bimatoprost SR administration, and were considered related to the study drug administration procedure. There were no reports of serious study drug-related adverse events, and no new safety concerns were observed after the second treatment. Please refer to the Investigator's Brochure for details on reported safety findings.

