11.3.5 Biomicroscopy and Ophthalmoscopy

Biomicroscopy will be performed in each eye by slit-lamp examination at each scheduled visit. Dilated ophthalmoscopy (including vitreous, optic nerve, macula, and retina periphery) and lens status assessment will be performed for each eye at Screening, Baseline, Week 12, Week 28, Week 44, Week 52, and Month 20/Exit.

All biomicroscopy and ophthalmoscopy examinations findings will be coded using MedDRA dictionary.

The number and percentage of patient eyes with biomicroscopy and ophthalmoscopy findings more than 1 severity grade increase (worsening, i.e., a change from 0 to 2 and above, or from 0.5 to 2 and above, or from 1 to 3 and above) from baseline for findings with a severity grade, or a status change from absence at baseline to presence at follow-up visit for findings under other pathology which is not associated with a severity grade, at 1 or more postbaseline visits, will be tabulated by preferred term in descending order of incidence rate. The number and percentage of eyes with any clinically significant findings will be presented (as "Overall") by treatment group for study eye and pooled for fellow eye. Similar analyses will be performed for each treatment cycle and may be provided for findings with other severity grade increase.

At follow-up visits, the lens opacity will be assessed only for eyes evaluated as phakic at baseline. The presence and severity of nuclear, cortical, and posterior subcapsular cataract lens opacities using a 3-point scale (absent, < standard photo #2, and \geq standard photo #2) will be summarized by treatment group for study eye and pooled for fellow eye by visit. The lens status will be presented as data listings and may be summarized with frequency and percent as necessary.

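### Visual acuity is tabulated only as each eye's worst change, overall and by cycle, so next-day loss after injection and lasting loss share a cell in most of the planned tables

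*SAP*

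**What the plan says.** SAP 11.3.2 sets the BCVA summary: "The data for the worst line change from baseline across follow-up will be summarized by treatment group" for study eyes, with fellow eyes pooled. It adds that "The worst line change is defined as the greatest decrease from baseline in the number of lines read". Eyes are then counted in three bands of lines: "worsening (< -2), no changes (≥ -2 and ≤ 2), and improving (> 2"). A last sentence adds the cycle tables: "Similar analyses will be conducted by treatment cycle". The section asks for no table at each visit or at the last visit, and has no rule that a loss must persist.

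On timing, Protocol 6.2 says: "Visual acuity tests will be performed at all scheduled visits except on any of the 3 administration days". The three Day 2 visits are therefore included. SAP 11.0 starts each cycle's data at its injection, so each cycle contains its own Day 2. SAP 11.0 also defines an extended follow-up period after Week 52, limited to patients with 3 injections.

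Two other parts of the SAP treat timing differently. SAP 11.1 separates "ocular TEAEs identified (onset or worsened) within 2 days of administration and identified more than 2 days". SAP 11.3.4 gives conjunctival hyperemia, which is assessed on the same visits as BCVA, a table at each scheduled visit as well as a worst-change table.

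**The concern.** Bimatoprost SR study eyes receive an intracameral needle injection. Control study eyes and all fellow eyes receive a needleless sham. Protocol 1.3.3 reports that most adverse events in the earlier study "occurred within the first 2 days after Bimatoprost SR administration". If some of those events lower acuity for a day or so, they would do so mainly in the implanted eyes.

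An implanted eye that is 3 lines down on Day 2 and back to baseline by Week 2 is then counted like an eye that has lost 3 lines for good. A raised rate in the implant arms could be put down to next-day blur, or blamed on lasting harm. The overall and Cycle 1 to 3 tables could not settle which. The worst of many tests also carries a noise background that grows with the number of tests and can dilute a small true rate of lasting loss.

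**Working it through.** **The SAP's worked example.** For 20/25 falling to 20/80, log10(20/80) rounds to -0.6 and log10(20/25) rounds to -0.1, so the change is 10 × (-0.6 + 0.1) = -5 lines. This matches SAP 11.3.2. With logs rounded to tenths, changes are whole lines, so worsening means 3 or more lines lost and improving means 3 or more gained.

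**Number of tests.** From the Protocol Summary visit schedule:
- Cycle 1: Day 2 and Weeks 2, 6, 12, 15 = 5
- Cycle 2: Day 2 and Weeks 18, 22, 28, 31 = 5
- Cycle 3: Day 2 and Weeks 34, 38, 44, 48, 52 = 6
- Extended follow-up: Months 14, 16, 18, 20 = 4

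The total is 20. It agrees with the protocol's 25 visits less Screening, Baseline and 3 administration days. Three of the 20 fall the day after an administration. None of the last 4 does.

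**Next-day loss.** The documents give no rate. If a transient 3-line Day 2 loss had probability p per injection, independently, the share of eyes with 3 injections that enter the worsening band from Day 2 alone is 1 - (1 - p)³. For assumed p of 2%, 5% and 10% this is 5.9%, 14.3% and 27.1%.

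**Noise.** The documents give no BCVA test error either, so an SD of 0.5 to 1.0 line is assumed. Take a stable eye whose true acuity t is uniform within a line. Baseline B and each follow-up F are t plus independent normal error, rounded to whole lines. With L = P(F ≤ B - 3 given t and B), the chance that the worst of n tests is worsening is the average of 1 - (1 - L)ⁿ over t and B.

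The last two columns come from a simulation of 400,000 eyes. There, a value 2 or more lines below the previous one is replaced by a fresh test, as a reading of the repeat rule in Protocol 6.2.

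| Assumed SD (lines) | Single visit | Worst of 4 | Worst of 5 | Worst of 20 | Worst of 20, with repeat | Single visit, with repeat |
|---|---|---|---|---|---|---|
| 0.5 | 0.05% | 0.2% | 0.2% | 0.7% | 0.3% | 0.03% |
| 0.7 | 0.8% | 2.5% | 3.0% | 7.9% | 3.9% | 0.4% |
| 1.0 | 4.2% | 12% | 14% | 29% | 17% | 2.4% |

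Rounding the difference instead of each test gives similar figures: 0.4% to 28.4% for the worst of 20 and 0.02% to 3.9% at the last visit, for SD 0.5 to 1.0.

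**Improving band.** Because it is applied to the minimum, an eye qualifies only if it gains 3 or more lines at every test. In the same model at SD 0.7, an eye truly 3 lines better throughout qualifies about 17% of the time over 20 tests, against about 69% at a single visit.

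**The case against.** A reader might infer that acuity is tabulated only over the whole of follow-up and that lasting loss cannot be told from next-day blur at all. The documents do not support that, for these reasons:

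- The cycle tables exist. If BCVA follows the periods in SAP 11.0, the extended follow-up table holds four tests, none of them shortly after an injection. Next-day loss cannot appear there and lasting loss should.
- SAP 16.3 puts all assessments in listings, and SAP 11.1 splits ocular adverse events at 2 days, so individual cases can be examined.
- Protocol 6.2 requires a repeat refraction and BCVA after a drop of 2 or more lines, which limits noise.
- Noise affects every arm, so Control shows its level.
- SAP 4.0 places table specifications in a separate document that is not available here.
- Day 2 loss would count against the implant, and injection-related loss is part of its real risk. A worst-change table is a legitimate sensitive screen.

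Much of this stands. It narrows the gap but does not close it:

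- The extended period leaves out patients without 3 injections. Protocol 5.10 allows readministration to be withheld because of earlier adverse events or safety concerns, so the excluded patients may be those of most interest. For a patient who misses the second or third injection, SAP 11.0 ends the cycle's data at the Week 15 or Week 31 window. A later loss then appears only in the overall table.
- Listings give no rate by arm, and adverse event tables depend on the loss being reported as an event.
- The repeat test does not remove a real next-day loss, and the documents do not say which value is analysed.
- SAP 16.3 defines an end-of-study assessment, but 11.3.2 asks for no BCVA table based on it.

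**Conclusion.** The point holds in a limited form. The tables committed to in the SAP give no arm-level rate of persistent acuity loss for all treated eyes. In the overall and Cycle 1 to 3 tables, next-day and lasting loss share a cell, and only the implant arms are exposed to needle-related next-day loss. The improving band, applied to a worst change, will leave out most eyes that truly improve.

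The size of the noise effect is uncertain. Stable eyes called worse over 20 tests range from about 0.7% to 29% without the repeat test, or 0.3% to 17% if the repeat value replaces the flagged one. Both ranges rest on an assumed SD of 0.5 to 1.0 line with independent errors. The Day 2 rates are illustrations. Protocol 1.3.3 reports early, mostly mild or moderate ocular events and does not say that acuity fell. Table 16-1 is not shown, so the Day 2 visit window could not be checked.

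No efficacy conclusion is affected, and the documents do not support reading the plan as hiding harm. This is a gap in descriptive safety reporting worth closing before the tables are produced.

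**What to change.** In SAP 11.3.2:
1. Keep the worst-change table. Split it into examinations within 2 days of an administration and later ones, as SAP 11.1 does for ocular adverse events.
2. Add the line change in the same three bands at each scheduled visit and at the last available visit, by treatment group, for all treated patients whatever their number of injections.
3. Report improvement from the by-visit and last-visit tables, not from the worst change.
4. State which value is analysed when a drop triggers a repeat test.

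The slit-lamp and ophthalmoscopy table in SAP 11.3.5 also counts findings "at 1 or more postbaseline visits, will be tabulated by preferred term in descending order of incidence rate". A 2-day split there would be consistent but is optional, since that table is already repeated by cycle.

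The cost is some SAP wording and a few more descriptive tables from data already collected. No assessment, visit or sample size changes.
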